estimate the probability of observing the data (or data more extreme) given that the null hypothesis is true; Bayesian analyses estimate the probability of the alternative hypothesis given the observed data (Wijeysundera et al 2009). Bayesian probability estimates incorporate prior information about plausible parameter values (i.e., the prior distribution) and the observed data (i.e., the likelihood). Combining these two distributions forms the posterior distribution which permits evaluation of the probability that the true value of the parameter falls in some range.

[figure not shown]
3. Primary Objectives

To assess the efficacy and safety of vadadustat for the prevention and treatment of ARDS in hospitalized patients with COVID-19

4. Study Design

This is a phase 2 multicenter, randomized, double-blind, placebo-controlled Bayesian clinical trial of vadadustat for the prevention and treatment of ARDS in hospitalized patients with COVID-19. Extended follow-up of participants will occur at 6, 12, and 24 months (see section 8.4.1).

Following screening, patients will be randomized in a 1:1 ratio to either vadadustat 900 mg or placebo. Randomization will be stratified by site, and MSOFA score at baseline (<4 and ≥4)

5. Study Outcomes:

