5.1. Assessment of Efficacy

5.1.1. Primary Outcome

The proportion of patients at day 14 who are dead (8) or hospitalized, on invasive mechanical ventilation or ECMO (7) or hospitalized, on non-invasive ventilation or high flow oxygen devices (6) on the NIAID-OS.

[figure not shown]

Table 4: National Institute of Allergy and Infectious Disease Ordinal Scale (NIAID-OS)

Death	8
Hospitalized, on invasive mechanical ventilation or extracorporeal membrane oxygenation (ECMO)	7
Hospitalized, on non-invasive ventilation or high flow oxygen devices	6
Hospitalized, requiring supplemental oxygen	5
Hospitalized, not requiring supplemental oxygen – requiring ongoing care (COVID19 related or otherwise)	4
Hospitalized, not requiring supplemental oxygen – no longer requires ongoing medical care	3
Not hospitalized, limitation on activities and/or requiring home oxygen	2
Not hospitalized, no limitations on activities	1
Source: https://clinicaltrials.gov/ct2/show/NCT04421027?cond=COVID19&lead=Lilly&draw=2&rank=1	•

5.1.2. Secondary Outcomes:

Proportion of patients with a score of 0 at 14 days on the MSOFA scale.

Organ System	0	1	2	3	4
Respiratory SpO2/FiO2	> 400	≤ 400	≤ 315	≤ 235	≤ 150
Liver	No scleral icterus or jaundice			Scleral icterus or jaundice	
Cardiovascular, hypotension	No hypotension	MAP < 70 mm Hg	Dopamine ≤ 5 or dobutamine any dose	Dopamine > 5 Epinephrine ≤ 0.1 Norepinephrine ≤ 0.1	Dopamine > 15 Epinephrine > 0.1 Norepinephrine > 0.1
CNS, Glasgow Coma Score	15	13 – 14	10 - 12	6 – 9	< 6
Renal, Creatinine mg/dL	< 1.2	1.2 – 1.9	2.0 - 3.4	3.5 - 4.9	> 5.0

Table 3: Modified Sequential Organ Failure Assessment (MSOFA) Score

Source: Grissom et al, 2010

Note: Discharged patients will be assigned a 0 score and dead patients a score of 20.

5.1.3 Other Outcomes:

• Average mSOFA scores at day 7 and day 14, gathered either from in-hospital labs and clinical notes for inpatients, or from calling discharged patients

- Ventilator-free survival at day 7 and day 14, as assessed by the patient's best score on the NIAID-OS on day 7, day 14 and day 28
- Overall survival at day 7, day 14 and day 28
- Proportion of patients with hypotension (MAP <70 mm Hg or requirement for inotropes or vasopressors to maintain blood pressure) at day 7 and day 14
- Proportion of patients with acute kidney injury at day 7 and day 14
- Time to hospital discharge

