6.1. Eligibility Criteria

6.1.1. Inclusion Criteria

- 1. Men and women ≥ 18 years of age
- 2. Laboratory-confirmed diagnosis of COVID-19 by detection of SARS-CoV-2 RNA by RTPCR from any specimen respiratory
- 3. Admitted to the hospital within 36 hours
- 4. For patients admitted WITH respiratory symptoms, enrollment must occur within 36 hours of hospital admission. If the patient is admitted to the hospital with normal saturations, but develops respiratory symptoms DURING their hospital stay, enrollment may occur within 24

hours of desaturation to 94% or less on room air.

- 5. Oxygen saturation of hemoglobin by pulse oximetry at room air $\leq 94\%$
- 6. Understands the procedures and requirements of the study and provides written informed consent and authorization for protected health information disclosure

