6.1.2. Exclusion Criteria

- 1. Hypersensitivity to vadadustat or any of its excipients
- 2. Placed on mechanical ventilation before randomization
- 3. Hemoglobin above the gender-specific upper limit of normal (ULN) at randomization: 16 g/dL for females and 18 g/dL for males
- 4. Patients who have erythrocytosis or polycythemia vera
- 5. Patient taking Probenecid, lopinavir or ritonavir.
- 6. Women who are pregnant or breastfeeding, or positive pregnancy test before randomization
- 7. Patients not on maintenance dialysis with eGFR<31ml/min.
- 8. Patients who have received a solid organ transplant, heart, kidney, liver or lung
- 9. Patients who are prisoners
- 10. Patients who are currently Do Not Resuscitate (DNR) or Do Not Intubate (DNI)
- 11. Patients with modified Rankin scale of 3 or greater
- 12. Patient who are currently enrolled in any other interventional clinical trial
- 13. Acute thromboembolism
- 14. Home oxygen (O2)

7. Study Drug

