8.1. Recruitment

All COVID-19 patients will be screened for eligibility. If a patient meets screening eligibility, the study coordinator will introduce the study to the patient to determine interest. If the patient is interested in participating in the study, the study coordinator will introduce the patient to one of the study clinicians either in person or virtually utilizing WebEx. Written consent will be obtained for all patients interested in study participation. Patients will be randomized if meeting all eligibility criteria (as specified in inclusion/exclusion criteria). Initial recruitment will occur at MHH-Southwest and MHH-Texas Medical Center for the first 30 patients. After 30 and then 120 patients are treated, screening and enrollment will be suspended (suspension of enrollment will occur at n = 30, based on DSMB recommendation, enrollment will continue during the safety analysis at n = 120) to enable an interim blinded safety analyses by the DSMB. The DSMB will provide a report to the UTHealth COVID-19 Research Workgroup and UTHealth IRB to consider further patient screening and enrollment.

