8.4. Data Collection

Refer to *Appendix 1 (Schedule of Activities)* for detailed timing and frequency of the below activities:

- Informed consent
- Demographic and contact information
- Oxygen saturation by pulse oximetry
- Pregnancy test (collected only at baseline)

٠

- Hemoglobin, creatinine, liver function test (AST, ALT, Bilirubin) at baseline, day 7, day 14 and during long term follow up visits at 6mo, 12mo and 24mo (If the patient remains hospitalized after 14 days, or the drug is discontinued for any reason, creatinine and hemoglobin lab values will be collected for up to 2 days following the last dose, again ceasing upon discharge.)
- Height, weight, BMI
- Eligibility, at baseline
- Randomization
- Blood biomarkers (during hospitalization only) \circ Baseline, Day 7 and Day 14 (10 cc each collection)
- Urine biomarkers (during hospitalization only)
 o Baseline, Day 7 and Day 14 (5 cc each collection)
- Medical/Medication history
- Study medication dosing
- AE and SAEs
- Concomitant medications and COVID-19 specific treatment other than vitamins and minerals
- Modified SOFA, daily until discharge, & at Day 7, 14, and 28, with discharged patients receiving a score of 0 and deceased patients receiving a score of 20.
- NIAID-OS, daily and until discharge and at Day 7, 14, and 28
- For patients who are discharged, before or after completing 14 days of in-hospital treatment, a phone visit at day 7, 14, and 28 after randomization will be conducted to collect serious adverse events and NIAID-OS score.

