13.1. Specific Statistical Hypothesis Primary Outcome

Among adult hospital admissions with lab-confirmed diagnosis of COVID-19, vadadustat 900 mg will demonstrate superiority to placebo as defined by a lower probability, at treatment day 14, of

death (8) or hospitalization, on invasive mechanical ventilation or ECMO (7) or hospitalization, on non-invasive ventilation or high flow oxygen devices (6) on the NIAID-OS. Generalized linear modeling will evaluate the probability of patients demonstrating this status at day fourteen of treatment as a function of treatment condition after covarying for stratification variables.

Secondary Outcome

Among adult hospital admissions with lab-confirmed diagnosis of COVID-19, vadadustat 900 mg will demonstrate superiority to placebo as defined by a higher probability, at treatment day 14, of recovery on the MSOFA scale (MSOFA = 0). Generalized linear modeling will evaluate the probability of patients demonstrating an MSOFA = 0 at day fourteen of treatment as a function of treatment condition after covarying for stratification variables.

[figure not shown]

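### The primary model carries baseline severity only as MSOFA below 4 versus 4 or more; prespecifying baseline NIAID-OS as a covariate is a cheap but modest gain in precision

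*Combined protocol and SAP*

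**What the plan says.** The primary outcome is NIAID-OS 6, 7 or 8 at day 14. Section 13.1 states that generalized linear modelling will "evaluate the probability of patients demonstrating this status at day fourteen of treatment as a function of treatment condition after covarying for stratification variables". Section 4 defines the variables: "Randomization will be stratified by site, and MSOFA score at baseline (<4 and ≥4".

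Category 6 of the outcome scale is "hospitalized, on non-invasive ventilation or high flow oxygen devices" (Section 5.1.1). On respiratory status at entry, Section 6.1.1 sets an upper limit of 94% on "Oxygen saturation of hemoglobin by pulse oximetry at room air", and Section 6.1.2 excludes patients "Placed on mechanical ventilation before randomization". High-flow oxygen is not excluded by name. The renal exclusion reads "Patients not on maintenance dialysis with eGFR<31ml/min", so maintenance-dialysis patients remain eligible.

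Section 8.4 collects "NIAID-OS, daily and until discharge and at Day 7, 14, and 28". Section 13.2 admits other baseline variables only if the arms differ (posterior probability above 95%) and the variable correlates with outcome. It then reports two sets of analyses, with and without the variable.

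Section 12 declares superiority if the posterior probability of a decrease of more than 2.5 points exceeds 0.85. The prior is Beta(1,1), or Normal with mean 0 and variance 10 on the coefficients when stratification factors are covaried.

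**The concern.** A patient who enters in category 6 is already in a state that the endpoint counts as failure, so baseline NIAID-OS should predict the outcome. The MSOFA cut carries part of that information through SpO2/FiO2, but it can misplace patients in both directions.

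- **Too low.** At SpO2 94% with no other organ points, FiO2 0.40 gives 94/0.40 = 235.0 and FiO2 0.62 gives 94/0.62 = 151.6. Both score 3, so the patient is in the lower stratum. The score reaches 4 only at FiO2 0.63 (94/0.63 = 149.2). One further organ point would also move the patient up.
- **Too high.** Creatinine above 5.0 alone scores 4, so a dialysis patient on low-flow oxygen can fall in the upper stratum.

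The Section 13.2 route does not recover this precision. It depends on an imbalance being flagged, and the resulting pair of analyses reads as a check on confounding, not as the primary result. What is at stake is some power if the true effect is smaller than planned, not validity.

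**Working it through.** **The plan's own figures.** With 325 per arm, power is approximately Phi((d - 0.025)/SE - 1.036), where SE = sqrt[p1(1 - p1)/325 + p2(1 - p2)/325]. With 25.1% on placebo:

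- d = 0.15: SE = 0.0293; Phi(4.27 - 1.04) = 99.9% (Section 12: 99.1%)
- d = 0.125: SE = 0.0303; Phi(3.30 - 1.04) = 98.8% (Section 12: 96.1%)
- d = 0.10: SE = 0.0312; Phi(2.40 - 1.04) = 91.4% (Section 12: 86.3%)
- d = 0: 3.8% type I error (Section 12: 3.5%, 4.8% and 3.7%, within the noise of 1,000 simulations)

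The stated powers fit better if 25.1% is the treated rate (99.2%, 95.9%, 85.5%). They also fit about 250-275 per arm. That mismatch is a separate matter, so the gains below are given for both readings of the rate.

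**Simulation inputs.** From the documents: N = 650, 1:1 allocation, 25.1% event rate, the 2.5-point and 0.85 rule, and Normal(0, variance 10) priors. The rest is assumed, because the documents give no baseline NIAID-OS mix, category-6 risk or total number of sites (Section 8.1 says only "Initial recruitment will occur at MHH-Southwest and MHH-Texas Medical Center for the first 30 patients"):

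- Share in category 6 and its day-14 risk: (10%, 35%), (10%, 60%), (20%, 45%), (20%, 60%), (25%, 50%), (30%, 45%), (30%, 60%), with 25.1% overall.
- Proportion with MSOFA 4 or more, category 6 versus the rest: 40% v 10%, 60% v 15%, 80% v 15%. This gives 7 x 3 = 21 settings.
- MSOFA odds ratio within category 1.5; 4 sites; site SD 0.3 on the logit scale; 10,000 trials per cell.

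Both models contain treatment, site and MSOFA stratum; the second adds baseline category 6. Each is a logistic model fitted by Laplace approximation and standardised to a risk difference.

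**Results, placebo rate 25.1% (range over settings).**

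| True effect (points) | Power without | Power with | Gain (points) |
|---|---|---|---|
| 15 | 99.9-100% | 99.9-100% | 0.0 |
| 12.5 | 98.7-99.5% | 98.7-99.8% | about 0 to 0.6 |
| 10 | 91.8-94.1% | 91.9-96.6% | -0.1 to 3.5 |
| 5 (added; not in Section 12) | 39.3-42.6% | 39.3-46.4% | 0 to 5.0 |
| 0 (type I error) | 3.3-4.1% | 2.8-4.1% | not inflated |

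At 10 points the variance of the risk difference falls by 0.2-20%. The equivalent extra sample is 650/(1 - cut) - 650: 650/0.9985 - 650 = 1 patient at the bottom and 650/0.7967 - 650 = 166 at the top. The grid median cut of 6.5% gives 650/0.935 - 650 = 45.

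If 25.1% is the treated rate, the gains at 15, 12.5 and 10 points are 0 to 0.5, 0 to 2.5 and -0.1 to 5.7 points.

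**Cross-checks.**

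- Varying sites (2 or 8) and site SD (0 or 0.6) in three settings gave a gain at 10 points of 0.0-4.2.
- A simpler simulation without site (3,000 trials per cell) gave, at 10 points, 91.7% to 91.8% in the weakest setting, 92.5% to 94.4% at (20%, 60%) and 93.8% to 96.8% at (30%, 60%).
- A different assumed grid put the further outcome variance explained (R2) at 1-17.5%, median 5%. Multiplying SE squared by (1 - R2) at 10 points moves 91.4% to 92.4% at R2 = 5%: Phi(0.075/(0.0312 x 0.975) - 1.036). At 17.5% it gives 94.6%.

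**The case against.** The strongest reply is that the plan already has a covariate-adjusted primary model whose severity measure includes SpO2/FiO2, and that nothing changes at the planned effect. That is true, and it is why this is an improvement rather than a defect.

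The top of the range also needs a very strong predictor. With 30% in category 6 at 60% risk, the rest have (0.251 - 0.30 x 0.60)/0.70 = 10.1% risk, an odds ratio of about 13. Settings with an odds ratio of 5 or less gained at most 1.5 points at 10 points. The grid was chosen by hand, so its medians describe the grid and do not estimate the gain in this trial.

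The share entering in category 6 is unknown and could be small. Enrolment is early, and the ventilation exclusion is not limited to invasive ventilation, so it could be read to cover non-invasive support. At 10% in category 6 with 35% risk there is no real gain. The too-low example fixes SpO2 at 94% and names no device; at SpO2 92% and FiO2 0.62 the ratio is 148 and the score is 4.

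Finally, Section 12's log-form wording may mean a log link, and Section 13.2 plans multilevel handling of site. The simulations used a logit link and fixed site effects.

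These points limit the size of the gain. They do not supply the missing covariate, and they identify no material loss from adding it.

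**Conclusion.** The concern holds as a modest, low-cost improvement. The primary result does not use baseline NIAID-OS, and the imbalance rule in Section 13.2 does not replace prespecification. Taking 25.1% as the placebo rate, the expected benefit is nil at 15 points, at most 0.6 points of power at 12.5, and between nothing and about 3.5 points at 10. The gain is somewhat larger if 25.1% is the treated rate. All of this depends on the assumed category-6 share, its risk and its overlap with MSOFA. In the grid, the worst loss of power was about 0.1 point, and type I error was not raised.

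**What to change.** 1. **Section 13.1:** prespecify one primary model with treatment, site, MSOFA below 4 versus 4 or more, and baseline NIAID-OS category (last score before first dose). Standardise its predictions over all randomised patients to obtain the absolute risk difference, and apply the 2.5-point and 0.85 rule to that posterior.
2. **Section 13.2:** replace imbalance testing as the trigger for adjustment with this fixed covariate. Label the unadjusted Beta(1,1) result and any analyses with other added covariates as sensitivity analyses.
3. **Section 12:** as a secondary clarification, state that the rule applies to the Section 13.1 model with the Normal priors. Section 13.1 already reads that way.

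Make the change before unblinding. It needs wording in three places and no new patients. Confirm that a pre-dose NIAID-OS is captured: Section 8.4 says daily without naming baseline, and the Appendix 1 schedule was not in the text reviewed. SpO2/FiO2 must already be known to assign the MSOFA stratum, so if the score is missing, the extra baseline item is the type of oxygen device. Re-running the Section 12 simulations under the amended model would be desk work.

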13.2. Bayesian Modeling Strategy

Initial analyses examining group differences for baseline variables will use cross-tabulation, ANOVA's, and examination of correlations between baseline variables and specified outcomes. For the purposes of evaluating the comparability of groups, a posterior probability of > 95% will constitute evidence for statistically reliable differences. Baseline or demographic variables on which group differences are detected, and which are correlated with outcomes, meet the definition of confounders (Assmann et al 2005, Pocock et al 2002) and will result in two sets of analyses: one in which the relevant variable is included as a covariate and one in which it is not. This will permit determination of the degree to which any group differences might confound conclusions regarding treatment.

Broadly, the data analytic strategy will use generalized linear and multilevel models (R v. 3.6, and Stan 2.17) for both discrete and continuous outcomes (SAS Institute 2002-2012, R Core Team 2017, Carpenter et al 2017). Multilevel generalized linear modeling to account for clustering of patients within site and repeated observations within patients will evaluate continuous, dichotomous, and count data. All analyses will apply intention-to-treat principles with missingness addressed via joint modeling of observed outcomes and the missing data, an approach robust to ignorable missingness (i.e., MCAR and MAR) (Best & Thomas 2000). Sensitivity analyses will evaluate robustness of analytic conclusions to missing data. Non-ignorable missing data patterns will be addressed through pattern-mixture modeling methods (Fitzmaurice & Laird 2000). Evaluation of posterior distributions will permit statements regarding the probability that effects of varying magnitudes exist, given the data. Specification of diffuse, neutral priors will reflect the initial uncertainty regarding effect sizes. For all generalized linear models, priors for regression coefficients will be specified as ~Normal ($\mu=0, \sigma 2=1 \times 10$), level one and two error variances will be specified as ~Half-Normal ($\mu=0, \sigma 2=1 \times 10^3$). The choice of prior distribution for level two variances will follow Gelman's recommendations (Gelman 2006). Priors for the comparison of proportions will be specified as ~Beta (α =1.0, β =1.0).

14. Ethics

The protocol titled "Vadadustat for the prevention and treatment of acute respiratory distress syndrome (ARDS) in hospitalized patients with Coronavirus Disease 2019 (COVID-19) will be

submitted to the local Institutional Review Board (IRB).

[figure not shown]
The protocol will be reviewed by:

The Committee for the Protection of Human Subjects The University of Texas Health Science Center at Houston

The study will be reviewed, approved and conducted in accordance with regulations mandated by The University of Texas Health Science Center at Houston Institutional Review Board. In addition, the study will be conducted according to the College of American Pathologists standards that meet Good Clinical Practice (GCP). These standards respect the following guidelines:

- GCP: Consolidated Guideline (International Conference on Harmonization ICH of Technical Requirements for the Registration of Pharmaceuticals for Human Use, May 1996)
- Integrated Addendum to ICH E6 (R1): Guideline for Good Clinical Practice, E6 (R2); Current step 4 version dated 9 November 2016.
- United States (US) Code of Federal Regulations (CFR) dealing with clinical studies (21 CFR Parts 50, 54, 56, 312, 314, and 511)
- Declaration of Helsinki, concerning medical research in humans ("Recommendations Guiding Physicians in Biomedical Research Involving Human Subjects,") Helsinki 1964, amended Tokyo 1975, Venice 1983, Hong Kong 1989 and revised version of Somerset West, Republic of South Africa, October, 1996, Note of Clarification added by the WMA World Medical Association General Assembly, Washington 2002, Note of Clarification added by the WMA General Assembly, Tokyo 2004

15. Informed Consent

Potential subjects are to receive a thorough explanation of study details and procedures and provided time to ask any questions. All subjects must sign the IRB approved informed consent form before performing any study-related activity (including screening activities). Due to COVID-19 to prevent cross contamination, the original signed consent form is given to the patient. A photograph using HIPAA compliant Tiger Connect will be captured of the signature page and will be placed in the subject's study file. In the case where an adult is incapable of making an informed decision, they will be excluded from study participation.

16. Data handling and record keeping

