2.6. COVID-19 and ARDS

7 - VSTAT | Revised December 23, 2021

[figure not shown]
Patients with COVID-19 present primarily with fever, myalgia/fatigue, or dry cough. In most cases, COVID-19 results in mild symptoms and patients can recover in 1 to 2 weeks. Most patients have a favorable prognosis; however, older patients and those with chronic underlying conditions may have worse outcomes. Patients with severe illness may develop dyspnea and hypoxemia within 1 week of onset, with the potential to progress to ARDS or end-organ failure (Wu et al, 2020). Typical findings of chest CT images of COVID-19 positive patients who are in the ICU include bilateral multiple lobular and subsegmental areas of consolidation. Analysis of 1324 laboratory-confirmed cases in Wuhan China showed that fever (87.9%) and cough (67.7%) were among the most common symptoms. Lymphopenia was observed in 82.1% of patients admitted to the ICU (Jin et al, 2020).

In a study of 5700 patients hospitalized with COVID-19 in New York City, the median age of patients affected was 63, with 39.7% female patients and 60.3% male patients. Common comorbidities included cancer (6%); cardiovascular disease, including hypertension (56.6%), coronary artery disease (11.1%), and congestive heart failure (6.9%); chronic respiratory disease, including asthma (9%), chronic obstructive pulmonary disease (5.4%), and obstructive sleep apnea (2.9%); immunosuppression, including HIV (0.8%) and history of solid organ transplant (1%); kidney disease, including chronic (5%) and end-stage disease (3.5%), and metabolic disease, including obesity (41.7%), morbid obesity (19%), and diabetes (33.8%). Among the 2634 patients who were discharged or died at the study endpoint, 373 (14.2%) patients were treated in the ICU, and 12.2% received invasive mechanical ventilation (Richardson et al, 2020). As of April 4, 2020, out of the patients requiring mechanical ventilation, 38 (3.3%) were discharged alive, 282 (24.5%) died, and 831 (2.2%) remained hospitalized. A total of 45 patients (2.2%) were readmitted during the study period.

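### Beyond the stratification factors, covariates are chosen by testing chance imbalance between randomised arms, and the plan does not say which of the two resulting analyses the 0.85 rule governs

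*Combined protocol and SAP*

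**What the plan says.** - **Allocation (Section 4).** "patients will be randomized in a 1:1 ratio", double-blind. "Randomization will be stratified by site, and MSOFA score at baseline", cut at 4.
- **Primary model (Section 13.1).** A generalized linear model of day-14 status "as a function of treatment condition after covarying for stratification variables". Site and baseline MSOFA are therefore always in it, balanced or not.
- **Decision rule (Section 12).** Superiority is declared if the posterior probability of a decrease greater than 2.5 points exceeds 0.85. Two prior forms are given: Beta(1,1), or Normal priors on coefficients when the stratification factors are covaried. No other covariate is mentioned.
- **Extra covariates (Section 13.2).** Arms are compared on baseline variables, and "a posterior probability of > 95% will constitute evidence for statistically reliable differences". Then: "Baseline or demographic variables on which group differences are detected, and which are correlated with outcomes, meet the definition of confounders". Such variables "will result in two sets of analyses": "one in which the relevant variable is included as a covariate and one in which it is not". The stated aim is to judge how far group differences might confound the treatment conclusion.
- **Not stated.** The candidate variables, a cut-off for being correlated with outcome, which set the 0.85 rule uses, and what follows if the sets disagree or several variables are flagged.

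**The concern.** With concealed 1:1 randomisation, a baseline difference between the arms as allocated is chance. A test for it returns its false-positive rate and says nothing about confounding in the causal sense. The second condition, correlation with outcome, can be checked only once outcomes are in hand, and the first needs arm labels. So the additional covariates are selected from trial results.

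The rule also looks in the wrong place for benefit. Adjusting for a prognostic variable gains precision whether or not it is imbalanced, yet here a balanced one is left out. Section 2.6 says that "older patients and those with chronic underlying conditions may have worse outcomes", but age is in no fixed model.

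What is at stake is whether one numeric success rule has one model to act on. If two sets are reported and fall on opposite sides of 0.85, the plan does not say which result stands.

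**Working it through.** **1. The plan's own figures.** Inputs from Section 12: N = 650 (325 per arm), placebo rate 25.1%, margin 2.5 points, threshold 0.85 (z = 1.036). Normal approximation: Pr(success) = Phi[(pC - pT - 0.025)/SE - 1.036], with SE² = [pC(1-pC) + pT(1-pT)]/325.

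- 15 points: SE = sqrt[(0.1880 + 0.0908)/325] = 0.0293. Phi(0.125/0.0293 - 1.036) = 99.9% (stated 99.1%).
- No effect: SE = 0.0340. Phi(-0.025/0.0340 - 1.036) = 3.8%; simulating the Beta(1,1) posteriors gives 3.6% (stated 3.5%). Monte Carlo SE with K = 1000 is about 0.6 points, so these agree.
- 12.5 and 10 points: 98.8% and 90.7-91.4% (stated 96.1% and 86.3%). These two do not reproduce, which is a separate matter.
- A 15% relative decrease would give only 24-26%, so the effect is in absolute points.

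**2. Chance of a flag.** Reading the 95% criterion in either direction, a balanced variable is flagged about 10% of the time. With k independent variables, Pr(at least one) = 1 - 0.9^k: 41% (k = 5), 65% (10), 79% (15), 88% (20). In one direction only (5% each): 23%, 40%, 54%, 64%.

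**3. Both conditions together, and the verdicts.** Simulation: 6000 trials with no effect and 3000 per effect size. The Section 13.1 model (treatment and MSOFA stratum; site not modelled) was compared with the same model plus all flagged variables. Both were linear risk-difference models with robust SE and a normal approximation to the posterior. Assumed, not in the documents: MSOFA ≥4 in 40% with log-OR 1.0, independent covariates, and |z| > 1.645 for both imbalance and outcome correlation.

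| Covariates (prognostic), log-OR per SD | Second set triggered | Opposite verdicts, no effect | 5-6 points | 10 points | Type I: Section 13.1 model alone; either set |
|---|---|---|---|---|---|
| 10 (5), 0.25 | 35-39% | 0.9% | 2.8-3.1% | 1.0% | 3.73%; 4.12% |
| 10 (5), 0.4 | 42-43% | 1.2% | 5.0-5.2% | 2.1% | 3.88%; 4.35% |
| 10 (5), 0.6 | 44-46% | 1.4% | 6.7-7.4% | 2.7% | 3.78%; 4.13% |
| 20 (8), 0.4 | 60-62% | 1.3% | 6.8-7.8% | 2.4% | 3.97%; 4.45% |

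Opposite verdicts are a share of all trials. Among triggered trials they occur in 2-3% (no effect), 8-17% (5-6 points) and 3-6% (10 points).

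A different set-up gives similar results: 15 variables, 2-3 of them prognostic at log-OR 0.3-0.7, logistic models with Normal(0,10) priors, 2000 trials per scenario. A second set arises in 40-56%, verdicts conflict in 4-6% of all trials at 6 points, and type I error rises 0.3-0.6 points if either set counts.

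**4. Precision from one fixed covariate such as age.** For a standardised covariate with log-OR b and mean event rate p, the SE is multiplied by about sqrt[1 - b²p(1-p)]. At a 6-point decrease p = (0.251 + 0.191)/2 = 0.221 and p(1-p) = 0.172.

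- b = 0.3: sqrt(1 - 0.0155) = 0.992, a 0.8% fall.
- b = 0.7: sqrt(1 - 0.0843) = 0.957, a 4.3% fall.
- Integrating the logistic curve, with MSOFA in the model as in step 3, gives 0.7% and 3.5%.

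Taking about 1-4% overall, the success probability at 6 points moves from Phi(0.035/0.0325 - 1.036) = 51.7% to 52.0-53.2% (SE multiplied by 0.993 and 0.965).

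**The case against.** The strongest reply is that the plan already has a deciding model. Section 12 gives priors for the 0.85 rule in two forms only, and the sole covariates it mentions are the stratification factors. Section 13.1 names that same adjusted model under the primary hypothesis. Section 13.2 gives the extra set a different job, judging possible confounding, which is what a robustness check does. Most of this stands and is the more natural reading. It is still an inference: Section 13.2 uses the sensitivity label for missing data a few lines later but not here, and Section 12 leaves the choice between its two forms open.

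A reader might infer three stronger things that the documents do not support:

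- **That covariates enter only through chance imbalance.** Site and baseline MSOFA are always in, and imbalance alone is not enough, since correlation with outcome is also required.
- **That the sponsor may pick the favourable set after unblinding.** Section 13.2 requires both to be run and provides for no choice between them. The type I figures for either set describe a practice that no section permits.
- **That the plan gives up a large amount of precision.** For one added covariate the gain is small (step 4).

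It is also fair to say that the conflicts matter mainly near the success boundary. At the planned effects of 10-15 points they are uncommon.

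**Conclusion.** The point holds in a limited form. Selecting extra covariates by testing imbalance between randomised arms is unsound, and the plan does not explicitly tie its success rule to one of the two analyses it then requires.

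The practical effect is modest. A second set is likely enough to plan for (roughly 35-60% of trials). Opposite verdicts are rarer: about 3-8% of trials at a true decrease of 5-6 points, 1-3% at 10 points, and about 1% with no effect. A rise in type I error of 0.3-0.6 points would leave it within the 3.5-4.8% that Section 12 itself reports, and it arises only if either set could be claimed.

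All these sizes depend on the number, strength and independence of the baseline variables and on reading the 95% criterion in either direction. The documents give none of these. The logical defect and the missing link between rule and model do not depend on them. The change is worth making because it costs almost nothing, not because the trial's conclusion is in serious doubt.

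**What to change.** 1. In Section 13.2, delete the imbalance test and the two-set rule. Present baseline comparability descriptively.
2. In Sections 12 and 13.1, state that the 0.85 rule applies to one model only: the Section 13.1 model with the stratification factors plus age, fixed in advance.
3. Include the baseline value of each laboratory outcome in its model. Section 8.4 already collects hemoglobin, creatinine and liver tests at baseline.
4. Label every other version, adjusted or unadjusted, as supportive, with no role in declaring superiority.

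The cost is analysis-plan wording; no new data are needed. The one constraint is that the covariates must be named before unblinding. If the sponsor wishes to keep the Section 13.1 model exactly as it stands, items 1 and 4 plus one sentence naming it as the deciding model still remove the ambiguity, and only the 1-4% reduction in SE is forgone.
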